PILOT CLINICAL STUDY PROTOCOL

Broccoli Extract Supplementation and Gastrointestinal Health in Older Adults with Active Alcohol Use and Low Diet Quality

IRB number

5106

IBC number

5063

Principal Investigator

[name]

Sub-Investigator

[name]

Sponsor

National Institute of Diabetes and Digestive and Kidney Diseases of the National
Institute of Health

Protocol Version

January 2024

Study Personnel

Principal Investigator

[name] - LSU Health Sciences Center, New Orleans, Louisiana.

Email: [contact]

Sub-Investigator

[name] - LSU Health Sciences Center, New Orleans, Louisiana.

Email: [contact]

Primary Mentor

[name] - LSU Health Sciences Center, New Orleans, Louisiana.

Email: [contact]

Secondary Mentors

[name] – Pennington Biomedical, Baton Rouge, Louisiana.

Email: [contact]

[name] – Tulane University, New Orleans, Louisiana.

Email: [contact]

SYNOPSIS

Study Purpose

To identify the effect of broccoli sprout extract (BSE) supplementations to mitigate alcohol-induced gut leak, inflammation, and oxidative stress.

Primary Objective

To test the ability of BSE to preserve gut barrier integrity. By assessing serum levels of biomarkers such as intestinal fatty acid-binding protein (iFABP), zonulin and lipopolysaccharide binding protein (LBP).

Secondary Objectives

To test the effect of BSE to decrease peripheral blood pro-inflammatory mediators. Isolated plasma will be assessed for pro-inflammatory cytokines (IFN-gamma, IL-2, IL-10, and TNF, IL-4, IL-6 and IL-17). To test the effect of BSE to decrease oxidative stress in peripheral blood. We will measure serum levels of lipid peroxidation, as well as enzymatic and non-enzymatic antioxidants.

Study Design

This will be a prospective, randomized, double-blind placebo-controlled clinical pilot study.

Study Date Range and Duration

January 2024, through January 2025.

Number of Study Sites

01 - LSU Health School of Medicine, [name].

Primary Outcome Variable

iFABP concentration.

Secondary Outcome Variables

IL-6 and total antioxidant capacity.

Study Population

Subjects \geq 50 years of age at enrollment, with active alcohol drinking and low diet quality.

Number of Participants

40.

Study Schedule

1. Remote Screening and Invitation to Participate (estimated time = 10 minutes)
2. Informed Consent and First Visit (estimated time = 4 hours)
3. Second Visit (estimated time = 4 hours)

Contents

SYNOPSIS.....	3

2.1 Background

Aging is associated with an increased risk of comorbidities. The close connection between nutrition, intake of bioactive nutrients/supplements, and inflammation validates the key role of dietary strategies as regulators of the immune response and inflammatory status^{1, 2}. Age-related changes in physiology and lifestyle can lead to decreased intestinal enzymatic activity and changes in the gut epithelium and microbial communities, contribute to nutrient malabsorption and gut barrier integrity disruption^{3, 4}. According to the National Survey on Drug Use and Health (NSDUH, 2020), the prevalence of alcohol use disorder (AUD) has increased in the last 20 years in older adults in the U.S. AUD has been linked to a broad spectrum of medical conditions with tissue and organ injury, including gastrointestinal-related diseases⁵. Chronic alcohol consumption leads to perturbations in gut microbiome balance (dysbiosis) and disruption of gut barrier integrity⁶. As a result, *bacteria, toxins, and metabolites can enter the blood stream and reach distant organs, triggering inflammation and oxidative stress*^{5, 7}. Through this mechanism gut leak is closely related to the onset of metabolic diseases, such as nonalcoholic fatty liver disease (NAFLD) and diabetes.

Intestinal barrier integrity can be evaluated in clinical, using serum biomarkers such as zonulin, iFABP/FABP2 (intestine fatty acid binding protein) and LBP (Lipopolysaccharide Binding Protein). Zonulin is a modulator of intracellular tight junctions (TJ), and increased zonulin serum concentrations correlates with intestine permeability. Whereas iFAB is present inside of the intestinal epithelial cells, transporting and regulating fatty acid absorption, and it is widely accepted as a biomarker of epithelial injury⁸. LBP has a key role in inflammation, by binding to bacterial lipopolysaccharide and triggering immune responses⁹. Despite the prominent role of diet and alcohol in the pathogenesis of metabolic diseases, there is a lack of treatments to mitigate their effects in triggering systemic inflammation and oxidative stress. *Novel treatments using generally recognized as safe (GRAS) compounds focused on restoring the intestinal barrier to mitigate metabolite endotoxemia are sorely needed.* This project will test the potential of broccoli sprouts extract (BSE) as a GRAS treatment to minimize the combined effect of poor nutrition and alcohol on the gut. Broccoli sprouts are rich in sulforaphane, a bioactive compound derived from the glucosinolate glucoraphanin with anti-inflammatory and antioxidant properties¹⁰. BSE supplementation has been used in preclinical and clinical studies as a health-promoting food, showing significant positive changes in the gut microbiota composition, protection against colitis, cardiometabolic improvement, and lower inflammation¹¹⁻¹³. We believe that BSE is a viable alternative therapeutic approach for patients who are resistant to lifestyle changes such as healthy eating and reducing alcohol use.

2.2 Purpose of Study/Potential impact

To test BSE supplementation in human subjects with poor nutrition compounded by alcohol use, specifically in older adults who we believe will receive greater benefit from this approach.

At the completion of the proposed study, we expect to have determined that treatments using generally recognized as safe (GRAS) compounds can be useful to restore the gut barrier integrity, and as consequence of reduced gut leak we expect to observe lower inflammation and oxidative stress.

2.3 Potential Risks

There are small, but real risks associated with some of the tests to be performed:

Interview & Completing Questionnaires: risks include emotional stress and fatigue.

Anthropometrics and Vital Sign: risk of fatigue, falls and device malfunction.

Phlebotomy: risk of discomfort and bruising. Some people may feel lightheaded or faint. There is also slight risk of infection.

Pills intake: risk of allergy, diarrhea or other gastrointestinal intolerance.

Unforeseen complications: there may be other complications that occur as a result of participation in this research study.

In order to minimize the potential risks, all the procedures will be performed by a trained professional, the materials and electronic devices to be used will be checked before the visits, sterile and single use materials for venipuncture, the participant's will be asked if they already consume vegetables from the Cruciferous vegetable's family (broccoli, arugula, bok choy, brussels sprouts, collard greens, cauliflower and cabbage).

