4.1.7 Eligibility Criteria

- Subjects ≥ 50 years of age at enrollment.
- Healthy Eating Index (HEI) score below 51 (poor diet).
- Consume at least 8 alcohol drinks/week. AUDIT-C score >8 .

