4.1.8 Exclusion Criteria

- Bowel-related diseases
- Diagnosed Diabetes

- Allergy or intolerance to broccoli.
- Any acute illness within the last 6 weeks.
- Chronic anti-inflammatory use or antibiotic treatment in the last 7 days.
- Acute illness withing the preceding six weeks (defined as fever, new antibiotic use or unscheduled healthcare visit – for illness).
- Acute alcohol intoxication upon arrival on the day of study visit.

Additional exclusion criteria:

- Any health issue that, the study investigator's judgement, confers excess risk for participation.

5. Study Methods

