5.2 Data Collection

We will use the REDCap (Research Electronic Data Capture) software toolset and workflow methodology designed for building and managing online surveys and databases to allow electronic data collection from multi-site clinical research studies. Data will be collected by interview and observer-assessments, and multiple levels of quality control will be used to ensure the highest level of data quality and security. The REDCap system allows for restricted access, read-and-write privileges for each database and data entry form. Routine data quality reports are produced evaluating range checks, valid fields, and missing fields. All changes to the database are logged and time stamped. In our prior work, the error rate was <1%. The participants will be randomized into placebo or BSE supplementation group, blood samples and data will be collected in two time-points, baseline day zero of treatment (Visit 1) and after 28 days of treatment (Visit 2). For the supplementation, the participants will be advised to take 2 capsules per day of the AVMACOL® (Nutramax Laboratories) supplement for a 28-days period. The placebo group will receive capsules with no BSE and will be instructed to take 2 capsules per day for the 28-days period.

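### The protocol body neither excludes current broccoli-sprout or sulforaphane supplement users nor asks participants to avoid starting these products, so the BSE–placebo contrast could be attenuated by an unknown amount

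*Combined protocol and SAP*

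**What the plan says.** Cruciferous intake comes up once as something to ask participants. Section 2.3 states that "the participant's will be asked if they already consume vegetables from the Cruciferous vegetable's family", in a sentence that begins "In order to minimize the potential risks, all the procedures will be performed by a trained professional". No threshold, action or repeat is attached to the answer.

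The diet criterion in 4.1.7 is "Healthy Eating Index (HEI) score below 51 (poor diet"). In 4.1.8 the broccoli-related exclusion is "Allergy or intolerance to broccoli", and the exclusion for concurrent agents is "Chronic anti-inflammatory use or antibiotic treatment in the last 7 days". Supplements are not mentioned in either list.

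Section 5.2 sets two capsules a day for 28 days in both arms and says "The placebo group will receive capsules with no BSE". It gives no instruction on outside intake. The reminders, weekly reports and pill count in 5.4 and 5.4.4 concern the study pills only. The adjustment set in 5.5 is sex, age, BMI, race/ethnicity and substance use.

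On mechanism, 2.1 says "Broccoli sprouts are rich in sulforaphane, a bioactive compound derived from the glucosinolate glucoraphanin with anti-inflammatory and antioxidant properties". The study cited there is, by its title, one of cruciferous vegetable intake and circulating proinflammatory markers.

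**The concern.** By the protocol's own rationale, the active compound can also be obtained outside the study capsules. The plan restricts some agents that could affect the outcomes (anti-inflammatories, antibiotics) but not products containing the test ingredient.

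Two routes could narrow the difference in iFABP change between arms:
- Someone already taking a broccoli-sprout or sulforaphane product may gain little more from BSE if the response saturates.
- A participant may start a comparable product between the visits. In the placebo arm this would produce part of the effect that the trial is trying to detect.

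Antioxidant supplements are a separate, smaller matter. They are not the active ingredient, but they bear on total antioxidant capacity, a named secondary outcome (4.1.4).

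If outside intake is not recorded at both visits, a null result cannot be told apart from lost contrast, and the information is hard to recover afterwards. That matters for a pilot whose result informs whether to go further.

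**Working it through.** **1. Is outside intake controlled or used anywhere in the protocol body?**

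| Place | Cruciferous intake | Broccoli-sprout or sulforaphane supplements |
|---|---|---|
| 2.3 Potential Risks | asked, for risk only | not mentioned |
| 4.1.7 / 4.1.8 eligibility and exclusions | HEI total only | not mentioned |
| 5.2 capsule instructions | not mentioned | not mentioned |
| 5.4 / 5.4.4 monitoring | not mentioned | not mentioned |
| 5.5 covariates | not mentioned | not mentioned |

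A current user is therefore eligible as written, and starting a product during the 28 days breaks no stated rule.

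**2. The plan's own sample size.** Section 5.5.1 gives 13 participants at power 0.8 and alpha 0.05, raised to 20 per group. It gives no effect size, SD, test or sidedness, and does not say whether 13 is per group or in total. The 13 therefore cannot be reproduced forward. Working backwards with a two-sided 5% two-sample t-test and 80% power, 13 per group implies a standardised effect of d = 1.145. With 20 per group, 80% power corresponds to d = 0.909.

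**3. Power if contrast is lost.** Let f be the fraction of the between-arm difference lost to outside intake. The documents give no value for f, so 10% to 30% is an assumption. The diluted effect is d × (1 − f). Power is from the two-sided 5% t-test at 20 per arm.

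| f | A: d = 0.909, diluted | Power A | B: d = 1.145, diluted | Power B | Sample multiplier 1/(1 − f)² |
|---|---|---|---|---|---|
| 0 | 0.909 | 80% | 1.145 | 94% | 1.00 |
| 10% | 0.818 | 71% | 1.031 | 89% | 1.23 |
| 20% | 0.727 | 61% | 0.916 | 81% | 1.56 |
| 30% | 0.636 | 50% | 0.802 | 70% | 2.04 |

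A assumes that the true effect is just large enough for 80% power at the planned size. B assumes that the 13 in 5.5.1 is per group and that its effect is true. Under B, power returns to 80% when f = 1 − 0.909/1.145 = 21%, so a loss of about one fifth uses up the margin gained by going from 13 to 20.

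**4. What f means in people.** If all the loss came from placebo participants obtaining the full effect elsewhere, f of 10%, 20% and 30% would mean 2, 4 and 6 of the 20.

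**The case against.** **The unseen appendices may cover it.** The schedule of activities and the questionnaires are in appendices not included in the text reviewed (5.1, 5.4), Visit 2 includes questionnaires (5.4.3), and scoring HEI requires some diet assessment. This stands: a reader might infer that intake is never recorded or used, but that is established for the protocol body only. A question in an appendix form would still leave the exclusion and covariate lists as they are.

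**Usual diet is a legitimate background.** The trial compares BSE capsules with capsules without BSE, in people with poor diets. Section 5.5 compares changes in each biomarker. Stable habitual intake is present at both visits, is balanced in expectation by randomisation and largely cancels in change scores. This stands too. It leaves mainly noise, with some chance imbalance possible at 20 per arm. It does not answer saturation in existing supplement users or products started after randomisation.

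**HEI below 51 already limits intake.** It may lower average vegetable intake, but it sets no limit on these foods and does not address supplements.

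**Placebo participants seeking the product.** It is tempting to infer that they will do so because the title names broccoli extract and 5.2 names a brand. The documents do not support this. The trial is double-blind, bottles are labelled by letter (5.5), and the text reviewed does not say that participants are told the brand.

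**Starting from 80% power at 20 per arm is pessimistic.** Fair: 5.5.1 puts 80% at 13. Both starting points are therefore shown, and both are assumptions.

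**Conclusion.** The gap is real in the protocol body: users of the test ingredient are eligible, nobody is asked to avoid starting it, and the one cruciferous question is tied only to risk. The expected consequence is attenuation through saturation or newly started products, plus some noise from habitual diet. Systematic bias from baseline diet is not expected.

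The size cannot be computed. The power figures rest on an assumed f of 10% to 30%, a two-sided t-test with 20 per arm, and one of two assumed effects. They show what a loss of that size would cost, not that it is likely.

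A stronger reading, that the placebo arm will take the active ingredient or that a null result is already uninterpretable, goes beyond the documents. So does treating antioxidant supplements as the active ingredient; their relevance is mainly to total antioxidant capacity. The change is worth making because it is cheap, whatever f turns out to be.

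**What to change.** - **Section 4.1.8:** add current use of broccoli-sprout or sulforaphane supplements as an exclusion.
- **Visit 1:** ask participants not to start these products or new antioxidant supplements, and to keep their usual cruciferous intake unchanged until Visit 2.
- **Both visits:** record cruciferous and supplement intake, including antioxidants, and report it by arm as the measure of achieved contrast. If the appendix forms already do this, cite them in the protocol body.
- **Section 5.5:** prespecify a sensitivity analysis of total antioxidant capacity that takes account of baseline antioxidant supplement use. This is preferable to a broad antioxidant exclusion, which would be hard to define and could screen out more people from a single-site convenience sample of 40.

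The cost is one exclusion line, one instruction and one short question repeated at Visit 2. A few supplement users would probably be screened out, though the documents give no figure for how many. No extra visits, assays or participants are needed.

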2.4 Potential Benefits

There will be no direct benefit to the participants of this study. However, this study will help the researchers and society to find strategies to mitigate alcohol effects in the gut.

3. Study Objectives

3.1 Hypothesis

Broccoli sprout extract (BSE) supplementation reduces gut leak and systemic biomarkers of inflammation and oxidative stress caused by alcohol consumption in older adults with unhealthy diets.

3.2 Primary Objective

To test the ability of BSE to preserve gut barrier integrity. By assessing serum levels of biomarkers such as intestinal fatty acid-binding protein (iFABP), zonulin and lipopolysaccharide binding protein (LBP).

3.3 Secondary Objectives

To test the effect of BSE to decrease peripheral blood pro-inflammatory mediators. Isolated plasma will be assessed for pro-inflammatory cytokines (IFN-gamma, IL-2, IL-10, and TNF, IL-4, IL-6 and IL-17). To test the effect of BSE to decrease oxidative stress in peripheral blood. We will measure serum levels of lipid peroxidation, as well as enzymatic and non-enzymatic antioxidants.

4. Study Design

4.1 General Design Description

This will be a prospective, randomized, double-blind placebo-controlled clinical pilot study. The participants will be recruited by convenience by printed advertising and word of mouth.

4.1.1 Study Date Range and Duration

January, 2024, through January 1st, 2025.

4.1.2 Number of Study Sites

01 - LSU Health School of Medicine, [name].

4.1.3 Primary Outcome Variable

iFABP concentration.

4.1.4 Secondary Outcome Variables

IL-6 and total antioxidant capacity.

4.1.5 Study Population

Subjects ≥ 50 years of age at enrollment, with active alcohol drinking and low diet quality.

4.1.6 Number of Participants

40.

4.1.7 Eligibility Criteria

- Subjects ≥ 50 years of age at enrollment.
- Healthy Eating Index (HEI) score below 51 (poor diet).
- Consume at least 8 alcohol drinks/week. AUDIT-C score >8 .

4.1.8 Exclusion Criteria

- Bowel-related diseases
- Diagnosed Diabetes

- Allergy or intolerance to broccoli.
- Any acute illness within the last 6 weeks.
- Chronic anti-inflammatory use or antibiotic treatment in the last 7 days.
- Acute illness withing the preceding six weeks (defined as fever, new antibiotic use or unscheduled healthcare visit – for illness).
- Acute alcohol intoxication upon arrival on the day of study visit.

Additional exclusion criteria:

- Any health issue that, the study investigator's judgement, confers excess risk for participation.

5. Study Methods

5.1 Study procedures

Study procedures are listed in the Schedule of Activities (Appendix 2).

5.2 Data Collection

We will use the REDCap (Research Electronic Data Capture) software toolset and workflow methodology designed for building and managing online surveys and databases to allow electronic data collection from multi-site clinical research studies. Data will be collected by interview and observer-assessments, and multiple levels of quality control will be used to ensure the highest level of data quality and security. The REDCap system allows for restricted access, read-and-write privileges for each database and data entry form. Routine data quality reports are produced evaluating range checks, valid fields, and missing fields. All changes to the database are logged and time stamped. In our prior work, the error rate was <1%. The participants will be randomized into placebo or BSE supplementation group, blood samples and data will be collected in two time-points, baseline day zero of treatment (Visit 1) and after 28 days of treatment (Visit 2). For the supplementation, the participants will be advised to take 2 capsules per day of the AVMACOL® (Nutramax Laboratories) supplement for a 28-days period. The placebo group will receive capsules with no BSE and will be instructed to take 2 capsules per day for the 28-days period.

5.3 Adverse Events Definition and Reporting

Adverse event means any untoward medical occurrence associated with the use of an intervention in humans, whether or not considered intervention-related (21 CFR 312.32 (a)). An adverse event (AE) or suspected adverse reaction is considered "serious" if, in the view of either the investigator or sponsor, it results in any of the following outcomes: death, a life-threatening adverse event, inpatient hospitalization or prolongation of existing hospitalization, a persistent or significant incapacity or substantial disruption of the ability to conduct normal life functions, or a congenital anomaly/birth defect. Important medical events that may not result in death, be life-threatening, or require hospitalization may be considered serious when, based upon appropriate medical judgment, they may jeopardize the participant and may require medical or surgical intervention to prevent one of the outcomes listed in this definition. The following guidelines will be used to describe severity of adverse events (AEs).

- **Mild** — Events require minimal or no treatment and do not interfere with the participant's daily activities.

- **Moderate** — Events result in a low level of inconvenience or concern with the therapeutic measures. Moderate events may cause some interference with functioning.
- **Severe** — Events interrupt a participant's usual daily activity and may require systemic drug therapy or other treatment. Severe events are usually potentially life-threatening or incapacitating. Of note, the term "severe" does not necessarily equate to "serious".

All adverse events (AEs) will have their relationship to study activities assessed by a study investigator who examines and evaluates the participant based on temporal relationship and his/her clinical judgment. The degree of certainty about causality will be graded using the categories below. In a clinical trial, the study product must always be suspect.

- **Definitely Related** — There is clear evidence to suggest a causal relationship, and other possible contributing factors can be ruled out. The clinical event, including an abnormal laboratory test result, occurs in a plausible time relationship to study activities and cannot be explained by concurrent disease or other drugs or chemicals. The event must be pharmacologically or phenomenologically definitive, with use of a satisfactory rechallenge procedure if necessary.
- **Probably Related** — There is evidence to suggest a causal relationship, and the influence of other factors is unlikely. The clinical event, including an abnormal laboratory test result, occurs within a reasonable time after study activities and is unlikely to be attributed to concurrent disease or other drugs or chemicals.
- **Potentially Related** — There is some evidence to suggest a causal relationship (e.g., the event occurred within a reasonable time after study activities). However, other factors may have contributed to the event (e.g., the participant's clinical condition, other concomitant events). Although an AE may rate only as "possibly related" soon after discovery, it can be flagged as requiring more information and later be upgraded to "probably related" or "definitely related", as appropriate.
- **Unlikely to be related** — A clinical event, including an abnormal laboratory test result, whose temporal relationship to study activities makes a causal relationship improbable (e.g., the event did not occur within a reasonable time after study activities) and in which other drugs or chemicals or underlying disease provides plausible explanations (e.g., the participant's clinical condition, other concomitant treatments).
- **Not Related** — The AE is completely independent of study activities, and/or evidence exists that the event is definitely related to another etiology. There must be an alternative, definitive etiology documented by the clinician.

The Study Investigator will be responsible for determining whether an adverse event (AE) is expected or unexpected. An AE will be considered unexpected if the nature, severity, or frequency of the event is not consistent with the risk information described in the informed consent form for the study intervention.

The investigators will record nonserious adverse events and report them to the sponsor regulatory agencies following the site's IRB guidance but no later than 7 days after the investigator becomes aware of the AE. The study principal investigator will immediately report any serious adverse event, whether or not considered study activities related, including those listed in the protocol or informed consent and must include an assessment of whether there is a reasonable possibility that a study activity caused the event.

All serious adverse events (SAEs) will be followed until satisfactory resolution or until the site investigator deems the event to be chronic or the participant is stable. Other supporting documentation of the event may be requested by the study sponsor and should be provided as soon as possible.

